## **Timeline and Estimated Costs**

We will continue enrollment until 100 patients complete their second wound care follow up and estimate this will take approximately 1 year. We anticipate enrollment of about 130 patients. Microdermis will provide Provodine at no cost to the patients.

## **Statistical Methods**

Continuously distributed outcomes will be summarized with the sample size, mean, standard deviation, median, minimum and maximum, and categorical outcomes will be summarized with frequencies and percentages. The number screened, the number of screen failures by reason, and the number randomized, and the number lost to follow-up by reason and the number completing the study by treatment group will be tabulated. Treatment groups will be contrasted with regard to cure (yes, no), new lesions (yes, no), and infections (yes, no) with Fisher's Exact tests. Adverse events, if any, will be listed by treatment group and case number and indicators of seriousness (serious, not serious), severity (mild, moderate, severe), and relation to the treatment (related to the treatment, unknown but not related to the treatment). All statistical testing will be two-sided with a significance level of 5%. The sample size was not derived from a statistical power calculation but was motivated by the pilot nature of this study. SAS Version 9.4 for Windows or R will be used throughout.

---

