### Study Design

We propose an open-label, randomized, pragmatic clinical trial for a pilot study to determine if Provodine can be used as an antiseptic and hand wash applied once daily to promote healing and improve outcomes in patients with skin abscesses and to reduce infections in their HCs. Patients will be randomized to Provodine or washing with soap and water. We have strategically selected our highest enrolling clinics from prior studies to start this investigation. If the results of this pilot study are promising, we will work with Microdermis to design and implement a follow-on statistically powered, clinical outcome study that will involve geographically distributed clinics and alternate sites around the US.

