The abscess cavity of both groups will be gently packed with  $\frac{1}{4}$  inch plain gauze strips and the wound will be covered with 4x4 gauze and secured with tape. Patients will be instructed to leave the wound packing in place and change the outer dressing once a day until they return at 48-72 hours for their first wound recheck.

Several studies have shown that there is no clinical benefit to antibiotics in the routine management of uncomplicated abscesses. Patients with uncomplicated abscesses (defined as palpable abscess < 5 cm in a healthy patient with no history of diabetes, HIV, IVDA or immunocompromised state who has no systemic signs of infection) will not be treated with antibiotics. Patients who do not meet these criteria will be treated with antibiotics at the discretion of the provider.

A study investigator will evaluate the patient in the emergency department or clinic within 48- 72 hours for the initial follow up visit and the packing will be removed. Patients randomized to Provodine will have the contents of the foil packet reapplied to the walls of the abscess cavity and surrounding skin. Data that will be collected on initial recheck include presence or absence of fever, purulent drainage, erythema, and pain, as well as presence of new skin lesions. A new lesion is defined as a new abscess, pustule, carbuncle, or furuncle at least 5 cm away from the initial wound. Lesions within 5 cm of initial wound will be considered failures of the initial abscess treatment.

Study investigators will also record compliance with intervention and side effects. Compliance will be assessed by measuring the amount of opened foil packets and by patient report. The cure rate, as measured by the absence of fever, pain, erythema and purulent discharge, will be recorded as well as the overall assessment by the provider if wound is improving, unchanged, or clinically worsened.

Wound management will be left up to the discretion of the treating provider, but further incision and drainage, wound repacking and antibiotic use will be reserved for patients determined to be not clinically improving or getting worse and will be considered a treatment failure. Outcomes including clinical cure, rate of new lesion development in patients and HCs, and therapeutic changes to clinical management will be recorded.

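### The adverse-event causality scale puts 'unknown' inside its only 'not related' value, so events of uncertain cause have no category of their own

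*Combined protocol and SAP*

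**What the plan says.** The Statistical Methods section of the combined protocol and SAP states the safety output in one sentence: "Adverse events, if any, will be listed by treatment group and case number and indicators of seriousness (serious, not serious", followed by "severity (mild, moderate, severe" and then "relation to the treatment (related to the treatment, unknown but not related to the treatment". Seriousness thus has two values, severity three and causality two.

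The Methods section covers collection only. At each of the two wound rechecks, "Study investigators will also record compliance with intervention and side effects". It gives no causality scale, no definitions and no rule for doubtful events. The Study Design section describes an "open-label, randomized, pragmatic clinical trial for a pilot study", so whoever judges causality can know the arm.

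**The concern.** A causality scale has to hold three kinds of judgement: the event is related, it is not related, or the assessor cannot tell. This one has a value for the first and a single value that mixes the other two. An assessor who cannot tell finds the word for that only in a label that also says the event is not related.

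Such events are foreseeable here. The product is applied to the walls and floor of an open abscess cavity and to the surrounding skin. Erythema and pain are both part of the cure definition, so a local reaction and a persisting infection can show the same recorded signs. Documented iodine sensitivity is an exclusion criterion, so sensitivity was considered in the design.

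At stake is what a reader can learn from the causality column. The pilot is meant to inform a larger powered study if its results are promising. A column that does not separate doubtful events from unrelated ones is a weak basis for planning safety monitoring in that study.

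**Working it through.** No arithmetic applies. The plan states no adverse-event rate or count, and no sample-size formula bears on the point. The check is whether each kind of event has a valid place under each plausible reading of the two values.

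**Inputs**
- Causality values: two (Statistical Methods).
- Definitions of those values, or a rule for uncertain events: none in Statistical Methods, Methods or any other section.
- Use of the causality value in a planned test: none. The Fisher's exact tests named in Statistical Methods compare cure, new lesions and infections.

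**Readings**
- Reading A, literal: the second value holds both unknown and not-related events.
- Reading B: the second value means that the cause is unknown but the event is judged not related.
- Reading C: the text is a slip for three values, namely related, unknown and not related.

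| Assessor's judgement | Reading A | Reading B | Reading C |
|---|---|---|---|
| Related | first value | first value | related |
| Cannot tell | second value, labelled not related | no value | unknown |
| Not related, other cause known | second value, although the cause is not unknown | no value | not related |
| Not related, cause not identified | second value | second value | not related |

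**Result**
- Under A, uncertain events carry a label saying not related, and events with a known other cause fit only if part of the label is ignored.
- Under B, two of the four judgements have no value.
- Under C every judgement has a place, but the printed text does not say this, and a data field built from it would carry two values.
- The number of values that hold an uncertain relation without also calling it not related is 0 of 2.

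**Reach.** Suppose *k* events are of uncertain cause. The number of them shown as not related can lie anywhere from 0 (assessors choose related each time) to *k* (assessors choose the second value each time). The documents give no figure for *k*. Whatever it is, the number of events listed in each arm is unchanged, because no step drops an event on its causality value.

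**The case against.** The strongest reply is that this is a wording slip with little consequence. Several parts of it stand.

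- **No rule sends doubtful events to the second value.** A reader might infer that every event of uncertain cause will be recorded as not related to Provodine. The documents do not support that. An investigator may choose related, and under Reading B a doubtful event has no value at all. The scale also refers to the treatment, and the listing covers both arms.
- **No analysis of related events is planned.** A reader might infer that the trial will report too few treatment-related events in the Provodine arm. The plan names a listing, with no specified count, rate or test of related events. Every recorded event appears under its arm, so the randomised comparison of events does not depend on causality.
- **Loss of the information is not shown.** A reader might infer that the distinction could never be recovered. No adverse-event form is among the documents, so its fields are not known. With events listed by case number and about 130 patients expected, going back to individual cases is feasible.
- **Some local signs are captured elsewhere.** Pain, erythema and purulent drainage are recorded at both rechecks in all patients and enter the cure comparison without a causality judgement. This does not cover every reaction; irritation of the hands is one example it misses.
- **Pooling unknown with related events is a convention.** Nothing in the documents requires it. A table of patients with any event by arm is a separate request, and the general statement that categorical outcomes are summarised with frequencies and percentages arguably allows it already.

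These points limit the consequence but do not repair the scale. The kindest reading, that three values were intended, still calls for a correction to the text.

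**Conclusion.** The concern holds in a limited form. The scale is defective as written: an event of uncertain cause is either labelled not related or has no valid category, and an event with a known other cause has no clear one. The causality column of the only specified safety output can therefore understate possible relation to treatment.

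The size cannot be computed from the documents. The effect on the planned tests is nil, and events can still be compared by arm. The open-label design adds some weight, because an ambiguous label leaves doubtful cases to assessors who can know the arm.

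The conclusion assumes that the data field will follow the text and that no definitions exist in a form or manual outside these documents. If such a form already separates the values, only the sentence in Statistical Methods needs correcting. The change is worth making, preferably before data are collected, but it does not threaten the efficacy results.

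**What to change.** In Statistical Methods, replace the two causality values with at least three separate ones: related; possibly related or unknown; not related. Define each in a sentence, and make clear that an event with a known other cause belongs under not related. Use the same values in the matching data field, and show the unknown events as their own category in the listing so that readers can group them as they see fit.

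The cost is one line of text, one data field and slightly more recording work, with no added patients or visits. The downside is that some events may move out of not related, so the listing may look slightly less favourable. If events have already been recorded on the two-value scale, those cases would need to be reviewed individually.
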